### b) Introduction:

### Poor oral health leads to poor general health and well-being

Oral diseases draw much attention from researchers, health professions, and policy makers recently. Poor oral health has a profound effect on general health [1]. Oral disease has become one of the most common non-communicable diseases, as they affect people throughout their lifetime, causing pain, distress, and even death. Moreover, the oral disease has negative social impacts (e.g., stigma and social isolation [2]) and adverse consequences on quality of life [3], while their treatment places a considerable economic burden on individuals, communities, and countries.

## Investments in adolescent's oral health bring substantial and sustainable effects

Oral health programs targeting adolescents can produce substantial and sustainable effects. Adolescence, as a transitional stage from children to adult, is a critical period to establish personality, develop knowledge/skills, and form healthy behaviour [4]. Thus, intervening in this critical period can produce substantial effects. In addition, investments in adolescent's health bring triple effects; as these investments protect the health of adolescents themselves at now, prevent health problems in their adulthood, and lay the foundations for their offspring's health in the future. Therefore, implementing interventions addressing determinants of healthy oral behaviours among adolescents has significant public health implications.

#### Hong Kong adolescents are vulnerable to oral disease

Hong Kong (HK) adolescents are especially vulnerable to oral diseases due to unmet service needs and unsatisfactory oral behaviours. Adolescents are at a risk for late diagnosis and treatment of oral diseases due to the discontinuances of free dental check-up service provided by HK government. Only primary school students (aged 6–11) in HK are eligible for free annual dental check-up. After being promoted to secondary school, students need to take care of their own dental health. A recent survey reported that two-thirds of HK adolescents did not visit dentists after promoting to secondary school [5]. Moreover, adolescent's service needs for oral diseases prevention is unmet due to a shortage of oral health care workers. HK has only 2224 registered dentists to serve a total of 7,374,900 residents (including 335,889 adolescents in secondary schools) [6]. The dentist to population ratio is about 1:3300, which is far from sufficient. The Faculty of Dentistry of the University of Hong Kong is the sole local university to provide 6-year undergraduate training in dentistry, and specialty training requires at least a further 6 years. In such circumstance of lacking professional dentists, oral health needs.

Healthy oral behaviour among HK adolescents is unsatisfactory. For example, dental flossing has not become part of adolescents' daily practice; that only 6.8% of 12-year students used dental floss daily [5]. Tooth brushing, as an effective and easily sustained healthy oral behaviour, is also unsatisfactory; that there were 30% of adolescents reported tooth brushing less than twice a day [5]. These poor oral behaviours cannot prevent oral diseases effectively.

As a result of the above vulnerabilities, HK adolescents are at a high risk of oral diseases and associated consequences. It was quite disappointing that less than 40% of HK adolescents (13-18 years old) were caries free and less than 10% had 'healthy' periodontal status. The prevalence of severe periodontitis increased progressively from 42% in 12 years through 56% in 15 years to 68% in 18 years old [7]. Oral diseases also substantially affected children's and their families' oral related quality of life, such as missing school due do pain or treatment, avoiding smiling and being teased by peers, and parent's feeling of upset, frustrated and guilty [8]. Overall, these susceptibilities to oral diseases among HK adolescents highlight their needs for oral health promotion programs.

## Existing evidence on interventions to promote oral health

A recent Cochrane review (2016) identified several community-based oral health promotion interventions under a range of health promotion strategies (e.g., educational activities, supervised tooth brushing programmes, motivational interviewing) targeting children [9]. The majority of the previous oral health interventions were health education in nature. These educational programs were able to produce short-term improvements in oral health knowledge, but they had limited effects on behavioural and clinical outcomes [10].

In addition to oral health education, motivational interviewing (a patient-centered approach focusing on building intrinsic motivation for change) was a newly developed strategy and was found to be more effective than health education strategy in eliciting positive changes in adolescents' oral health behaviours [11]. Each participant joined a one-by-one, face-to-face motivational interviewing session with an expert at first; then they received five follow up telephone calls from the expert to maintain the change and avoid relapse. Although effective, this motivational interviewing strategy was an expensive one as it took much time to complete the first interviewing one-by-one and required follow up calls to sustain the effect. The cost-effectiveness of the motivational interviewing strategy was not fair enough.

Local organizations in HK also make great efforts in promoting oral health among children and adolescents. The Oral Health Education Unit, Department of Health, the Government of HKSAR [12] is the main body which aims at promoting oral health to the public through educational and promotional activities. The majority of the current services target at primary school children (e.g., School Dental Care Service), not secondary school adolescents. Notably, this unit started a "Teens Teeth Programme" that aimed at promoting oral health among secondary school students in 2005. This program enrolled S1 students and focuses on reducing gum bleeding and supporting flossing habit. However, a wider range of oral diseases and behaviours (e.g., dental visit for check-up) need to be covered, and S1 students might have limited capacity in conducting health promotion programs as leaders. Overall, despite the great efforts that health professionals and governmental officers have made to improve oral health among adolescents, the prevailing oral health needs among HK adolescents are still unmet. Specific oral health promotion programs targeting adolescents are still needed.

## Theory-based intervention to modify adolescent's cognitions

Healthy oral behaviours can prevent oral diseases to a large extent, and cognitions play an increasingly important role in affecting oral behaviours among adolescents [13]. Previous studies have found a variety of cognitive variables that were associated with oral behaviours, such as self-efficacy, perceived benefits, and cues to action (e.g., a recommendation from dentists) [14].

Cognitive factors orientated by behavioural theories would be most effective in changing oral behaviours. Various theories have been applied to explain oral behaviour, including Theory of Reasoned Action, Health Belief Model, Health Action Process Approach, and Theory of Planned Behaviour (TPB) [14]. The health belief model (HBM) and the social cognitive theory (SCT) has been used to develop effective interventions to change health-related behaviours [15].

HBM is a psychological health behaviour change model which is developed to explain and predict health-related behaviours [16]. It prescribes that perceived susceptibility, perceived severity, perceived benefits, perceived barriers, and cues to action. A recent addition to the HBM is the concept of self-efficacy, which indicates one's ability to successfully perform an action. Perceived susceptibility is defined as one's opinion of chances of getting a condition. Perceived severity refers to one's opinion of how serious a condition and its sequences are. Perceived benefits refers to one's belief in the efficacy of the advised action to reduce risk or seriousness of impact. Perceived barriers indicates one's opinion of the tangible and psychological costs of the advised action. Cues to action are strategies to activate the readiness and stimulate overt behaviour. Self-efficacy denotes the confidence in one's ability to take action. Instruments based on the HBM has been validated and used to explain and predict oral health habits, oral hygiene, and periodontal parameters [17].

SCT is a learning theory based on the concept that people learn by observation. The theory deals with cognitive, emotional aspects and behavioural aspects for understanding behavioural change. Meanwhile, it provide ways for new behavioural research in health education [18]. The core concepts of this theory is reciprocal determinism which contains the following three determinants:

- (1) Personal: Whether the individual has high or low self-efficacy toward the behaviour.
- (2) Behavioural: The response an individual receives after they perform a behaviour.
- (3) Environmental: Aspects of the environment or setting that influence the individual's ability to successfully complete a behaviour [19].

HBM and SCT have been widely applied in various behaviours including oral health related behaviours [18, 20, 21]. Consistent findings have been reported that the core contents of these theories were all associated with healthy oral health related behaviours (e.g., tooth brushing). However, most of the previous applications were in cross-sectional studies, and the clear paths among cognitions, behavioural intention, and behaviours were less explored and confusing. Considering the wide application of HBM and SCT in the adolescent population [20, 21], further testing on its applicability with a longitudinal design among adolescents is promising.

## Peer-led programs to modify adolescent's cognitions

Peer-led health promotion programs have been widely implemented among the adolescent population. Its effectiveness in promoting adolescents' health has been proved with strong evidence [22]. For example, peer-led programs improved adolescent's health through reducing smoking, providing nutrition education and preventing risky sexual behaviours [22].

Peer-led health promotion programs have advantages over teacher-led programs or researcher-led programs. Compared to teachers/researchers, peers are more successful than teachers in passing on information because of their "insider" point of view [23]. Peers are also considered as a credible source of information. Moreover, peer leaders act as positive role models, which is an important component of the learning process (supported by Social Learning Theory). The successful experience of peer leaders helps their classmates to build up confidence, which is necessary to initiate behaviour change.

As one important component in providing peer support, the peer-led program is perfectly applicable to the adolescent population. Erikson's Psychosocial Development Theory states that, at the stage of adolescence, adolescents try to achieve a sense of identity regarding who they are and where their lives are headed. Peer leader functions as a real-world model and helps to build up a sense of identity or belonging. Such recognition makes the peer-led program more likely to achieve a profound effect on adolescents. Moreover, HK adolescents are under enormous stress [24] due to heavy load inside and outside of schools. Peer support is beneficial to help adolescents to cope with such stresses. Thus peer-led program with peer support has great potential to improve adolescents' health, including oral health.

## Knowledge gap identified

In summary, HBM and SCT are the most promising cognitive theory used to modify healthy oral behaviours, and peer-led health promotion programs are of highest effectiveness and feasibility. However, there is no previous study incorporating these two effective intervention components into one single study among adolescents. The efficacy of such kind of novel intervention has never been investigated in the domain of oral health.

The current study aims to fill this gap by testing the efficacy of a peer-led theory-based intervention in promoting healthy oral behaviours among adolescents in Hong Kong. With the longitudinal data, we are able to test a wide range of different (direct and indirect) effects and pathways, which is exactly the current case of involving personal cognitions, behavioural intentions, oral behaviours, and clinical oral health outcomes.

# c) Aims and Hypotheses to be Tested:

## Objectives

- The primary aim is to evaluate the relative efficacy of a peer-led theory-based intervention in promoting healthy oral behaviours versus the control (normal practice) on increasing the prevalence of healthy oral behaviours (tooth brushing, dental flossing, and dental visit for check-up) among adolescents in Hong Kong;
- 2) The secondary aim is to evaluate the relative efficacy of the intervention and control groups in affecting clinical oral health outcomes, including dental caries and periodontal health;
- The third aims are to evaluate the relative efficacy of the intervention and control groups in affecting secondary outcomes of thoery-based constructs including
   i) increasing paramined evaluate the intervention and control groups in
  - i) increasing perceived susceptibility towards oral diseases,
  - ii) increasing perceived severity towards oral diseases,
  - iii) increasing perceived benefits towards healthy oral behaviors,
  - iv) reducing perceived barriers of performing oral health behaviors,
  - v) provide cues to action related to oral health behaviors,
  - vi) build self-efficacy of performing oral health behaviors,
  - vii) provide social support and professional support of oral health knowledge,
  - viii) increasing outcome expecatations towards healthful oral behaviours.

## **Hypotheses**

- The hypothesis involving clinical oral health outcomes is that a lower prevalence of dental caries and better periodontal health status will be found in the intervention group than in the control group.
- 2) The hypothesis includes that a higher prevalence of healthy oral behaviours (of any type) will be found in the intervention group than in the control group.

- 3) The hypothesis based on the third outcomes states that the intervention group as compared to the control group will have a higher score in positive theory-based constructs towards healthy oral behaviours
- d) Plan of Investigation:
  - (i) Subjects

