## (iii) Study design

## Baseline survey and dental examination

The baseline survey will collect information on participants' background characteristics (e.g., socio-demographics), theory-based variables (perceived benefits, perceived barriers, perceived severity, self-efficacy and behavioural capability), and oral health behaviors. Validated scales have been identified and will be used in the survey [34, 35].

To comprehensively assess each participant's oral health status at baseline, their caries experience and periodontal condition will be recorded following the recommendations of the World Health Organization (WHO) for oral health surveys [36]. Oral hygiene status will be recorded through plaque index (PI) (Quigley Hein, 1972) on a scale of 0 to 5. Dental caries experience will be recorded by counting the numbers of permanent teeth that are decayed (DT), missing due to caries (MT), and filled (FT) to generate a DMFT score. Periodontal condition will be recorded using the Community Periodontal Index (CPI). Two trained and calibrated examiners (kappa = 0.81 - 0.87 for intra- and inter-examiner reliabilities for the assessment of DMFT and CPI) will perform the clinical examinations using a plane disposable plane intra-oral mirror with a built-in LED light source and a WHO CPI periodontal probe. Ten percent of the participants will be randomly selected and re-examined in each school to continuously monitor intra- and inter-examiner reliabilities of assessing PI DMFT and CPI.

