The second follow-up at months 12 will include two parts. The first part is to collect participants' self-reported data through survey, the same procedure as the first follow-up at 6 months. The 12-month follow up data suggest a prolonged impact of the intervention, as no intervention activities will be conducted between months 6 and months 12.

The second part is to do dental re-examination, using the same methods and criteria as the baseline examination. We will compare the changes of the oral health status before and after the intervention. The consistency between self-reported healthy oral health behaviors and dental examination outcomes will also be calculated. No dental examination will be conducted at 6-month follow up, as oral health status is not likely to change much within a short time period like 6 months.

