## Outcome indicators and potential confounders

The primary outcome is the prevalence of performing each of the three types of healthy oral health behaviors, including tooth brushing, dental flossing, and dental visit. The increase in performing healthy oral behaviors is the key of public health significance. The secondary outcome is the prevalence and severity of oral diseases, including dental caries and poor periodontal status. The third outcome is the prevalence of theory-based constructs regarding the above healthy oral behaviors, including perceived benefits, perceived barriers, perceived severity, self-efficacy and behavioural capability.

Potential confounders include socio-demographic characteristics, pre-existing oral diseases, and utilization of dental services (except for dental check-up) during the follow-up period. Such information will be collected at the baseline and follow-up survey, and between-group differences will be tested for statistical significance. Any significant differences will be adjusted in the analysis evaluating the efficacy of the intervention as compared to the control group.

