## (iv) Data processing and analysis

The intra- and inter-examiner reliabilities of assessing PI, DMFT and CPI at the tooth level will be tested through the use of the kappa statistic. Data of DMFT and CPI at the tooth level will be used to generate the oral health status at the subject level.

Intention-to-treat analysis will be conducted. Multiple imputation methods will be used [40] to deal with missing data if it occurs. Between-group (intervention versus control) baseline differences in the frequency distributions of potential confounders will be compared by using chi-square test, t-test, Mann-Whitney test or other statistics. The absolute and relative risks and number needed to treat (and 95% confidence intervals) for the binary outcomes comparing the two groups at months 6 and 12 will be derived. Comparisons between the intervention and control groups will be made for all binary outcomes, adjusting for any potential confounders showing p<.10 in the between-group baseline comparisons (if any), using modified Poisson regression with robust sandwich variance estimation. SPSS will be used for data analysis; p<.05 (2-sided) will be taken as statistically significant. The research team is very experienced in performing data analysis.

Based on the number of intervention activities that the participants are actually exposed to, we will conduct a regression analysis to explore whether the incease of numbers of activities will increase the efficacy of the intervention. Subgroup analysis will also be conducted to compare the efficacy among participants who are exposed to different (or different combinations of) intervention activities.

We will consider the variables of oral health status at baseline, and test its mediating effect on the relationship between theory-based cognitions (and changes) and healthy oral behaviors (and changes). In statistics, a mediating effect can be tested by using an interaction term, whereby the effect of an independent variable on a dependent variable varies by the level of the mediator [41]. The mediating hypothesis is supported if the regression coefficient of the interaction term onto the dependent variable is statistically significant.

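### The caries hypothesis is month-12 prevalence on a cumulative index, and baseline disease is adjusted for only if it differs at p<.10, so much of any preventive effect would be hidden

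*Protocol*

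**What the plan says.** Under Hypotheses, the protocol expects that "a lower prevalence of dental caries and better periodontal health status will be found in the intervention group than in the control group". Caries is measured (Baseline survey and dental examination) by "counting the numbers of permanent teeth that are decayed (DT), missing due to caries (MT), and filled (FT) to generate a DMFT score". Teeth are examined at baseline and month 12 only.

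Outcome indicators and potential confounders is wider than the hypothesis: "The secondary outcome is the prevalence and severity of oral diseases, including dental caries and poor periodontal status". The section on the month-12 follow-up adds: "We will compare the changes of the oral health status before and after the intervention". Neither place names a caries increment or an incidence measure.

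Data processing and analysis states one between-group model: "Comparisons between the intervention and control groups will be made for all binary outcomes", by modified Poisson regression with robust variance. Covariates enter only if they differ between arms at baseline at p<.10. Pre-existing oral disease is on the list of potential confounders, so baseline caries and periodontal status fall under that rule.

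As background, the introduction reports that "less than 40% of HK adolescents (13-18 years old) were caries free".

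**The concern.** DMFT counts decayed, missing and filled permanent teeth over a lifetime. Apart from examiner error, a student who scores above zero cannot return to zero. If a caries case is DMFT above zero, the intervention can change status only among students who are caries-free at baseline. The rest add the same fixed block to both arms, together with the chance difference in baseline prevalence between two sets of six schools.

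Two things are at stake. A real reduction in new caries may be reported as no effect on caries prevalence. A chance baseline difference too small to trigger adjustment may also be carried into the month-12 comparison, in either direction.

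**Working it through.** **No plan figure to reproduce.** The sample size section covers tooth brushing only. The protocol gives no expected effect, incidence, ICC or power for caries.

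**Inputs from the protocol.** 390 students and six schools per arm; ICC 0.05 (set for tooth brushing); two-sided 5% test. I read the stated 85% as retention, which gives 390 × 0.85 = 331.5 analysed per arm, or 55.25 per school.

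**Assumptions.** A case is DMFT above zero. The brushing ICC also holds for caries. Baseline prevalence b is 60% or 40%: the introduction implies over 60% at ages 13-18, and S2 students may be lower. Twelve-month incidence among the caries-free is i = 20% or 10% under control, and is halved by the intervention.

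**Formulas.**
- Month-12 prevalence = b + (1 − b) × incidence.
- Design effect = 1 + (m − 1) × ICC, where m is the number per school.
- z = difference / √[(p₁q₁ + p₂q₂) / (n / design effect)].
- Power = Φ(z − 1.96) + Φ(−z − 1.96).

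**Unadjusted month-12 prevalence.** Design effect = 1 + 54.25 × 0.05 = 3.71, so the effective n is 331.5 / 3.71 = 89.3 per arm.
- b = 60%, i = 20%: 68% vs 64%; z = 0.04 / √(0.448 / 89.3) = 0.56; power about 9%.
- b = 60%, i = 10%: 64% vs 62%; z = 0.28; power about 6%.
- b = 40%, i = 20%: 52% vs 46%; z = 0.06 / √(0.498 / 89.3) = 0.80; power about 13%.

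**Incidence among students caries-free at baseline.**
- b = 60%: n = 132.6, m = 22.1, design effect 2.06, effective n 64.5. For 20% vs 10%, z = 0.10 / √(0.25 / 64.5) = 1.61, power about 36%. For 10% vs 5%, z = 1.08, power about 19%.
- b = 40%: n = 198.9, m = 33.15, design effect 2.61, effective n 76.3. For 20% vs 10%, z = 1.75, power about 42%.

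**Prevalence adjusted for baseline caries.** I simulated 12 schools with 60% baseline prevalence, 20% vs 10% incidence and ICC 0.05, analysed by modified Poisson regression. The typical z is about 0.56 without baseline caries in the model and about 1.5 with it. Adjustment alone therefore recovers most of the gap to 1.61.

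**Does the p<.10 rule secure that adjustment?** At baseline there are 390 per arm, with design effect 1 + 64 × 0.05 = 4.2 and effective n 390 / 4.2 = 92.9.
- Standard error of the chance imbalance = √(2 × 0.6 × 0.4 / 92.9) = 7.2 points.
- An ordinary chi-square test, which ignores schools, reaches p<.10 at 1.645 × √(2 × 0.6 × 0.4 / 390) = 5.8 points.
- At b = 60% the effect sought is 2 to 4 points (i = 10% to 20%).
- The rule triggers with probability P(|Z| > 5.8 / 7.2 = 0.80), about 42%, so in about 58% of trials there is no adjustment.
- An imbalance above 4 points that still goes unadjusted has probability P(|Z| > 0.56) − 0.42 = 0.58 − 0.42, about 16%.

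**The case against.** Much of the case on the other side stands.

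- **The outcome is not prevalence alone.** The outcome section names severity and the month-12 section names changes. Both can move in students who already have caries. A reader might infer that the secondary aim is bound to show nothing; the document does not support that. What remains is that the caries hypothesis, as worded, uses neither.
- **The ceiling does not reach periodontal status.** CPI and plaque index are not cumulative tooth counts. Only the conditional adjustment rule applies to them.
- **The case definition is assumed.** DT, MT and FT are recorded separately, and no case is defined. Untreated decay (DT above zero) could reverse, but through fillings as well as prevention, so it would not isolate a preventive effect.
- **The background figure is not this sample's.** A reader might infer that over 60% of the enrolled students cannot change status. The figure covers ages 13-18, and S2 students are at the younger end. At 40% prevalence power is still only about 13%.
- **Prevalence itself is not unusable.** Most of the loss comes from leaving baseline caries out of the model. The protocol already lists it as a confounder; the weakness is the condition attached.
- **No count model is stated.** That is commonly left to a statistical analysis plan and is not counted against the protocol here.

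**Conclusion.** The point holds in limited form. The protocol fixes together a prevalence hypothesis, a cumulative index, a binary model and a significance-triggered baseline adjustment. For a preventive intervention this wastes information that the trial will collect. Under the stated assumptions, halving new caries gives about 9% power at 60% baseline prevalence and 13% at 40%, against about 36% and 42% for incidence among the caries-free. With baseline caries always in the model, prevalence comes close to the incidence result at 60% baseline. The p<.10 rule does not secure that, because it stays silent for imbalances larger than the whole effect.

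These figures rest on DMFT above zero as the case definition, an assumed incidence, and an ICC borrowed from tooth brushing. They do not show that the whole clinical aim fails. Nor is low power for caries a fault in itself: it is a secondary outcome for which the trial was not sized, and it stays low after the change.

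**What to change.** In Data processing and analysis, always adjust the month-12 caries and periodontal comparisons for baseline DMFT and CPI, whatever the baseline p-value, with school clustering accounted for. In Hypotheses and in Outcome indicators and potential confounders, state the caries hypothesis as new disease over 12 months: the DMFT increment per student, and incidence among students caries-free at baseline, saying what counts as caries-free. Month-12 prevalence may stay as a baseline-adjusted supporting outcome.

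This costs nothing beyond wording. The baseline and month-12 examinations already supply the data, with no extra students or visits.
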